#### **6.1.6 REQUIRED Management of Possible Immune Response to the NSCs**

Participants who develop a grade 2 or higher Immune Response to NSCs, will take dexamethasone to a maximum dose of 4 mg twice daily until symptoms resolve to  $\leq$  Grade 1. For participants continuing to receive NSCs, dexamethasone should continue at a dose determined by the treating investigator and per consultation with the principal investigator. For participants no longer receiving NSC administration may continue dexamethasone at the discretion of the treating investigator and per consultation with the principal investigator.

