#### **Criteria for Removal from Participation or Treatment**

---

For participants who begin treatment, duration of therapy will depend on individual response, evidence of disease progression and tolerance. In the absence of treatment delays due to adverse events, treatment may begin and continue until or unless one of the following criteria applies:

- Pathology review of the frozen section obtained at the time of surgery does not confirm recurrent high grade glioma (Section 8.1). Such participants will not continue on to receive any study agents, and all study procedures will end.

- Participant does not meet the criteria for initiating irinotecan dosing following surgery (Section 7.2.3). During cycle 1, if a participant requires more than 16 mg/day of dexamethasone to control cerebral edema at the time s/he is ready to begin treatment with irinotecan, then s/he will be considered neurologically unstable and will not continue with study treatment; however, the patient will still be evaluable for toxicity.
- Evidence of disease progression.
- Unacceptable adverse event(s) (see Section 7.2).
- Intercurrent illness that prevents further administration of treatment.
- Participant needs a treatment not allowed by the protocol.
- A participant may always be removed from treatment whenever s/he wishes.
- General or specific changes in the participant's condition render the participant unacceptable for further treatment in the opinion of the treating investigator.

Participants will be removed from study treatment when any one of the criteria listed above applies. The reason for study treatment removal and the date the participant was removed must be documented. Alternative care options will be discussed with the participant.

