### 6.1 Prophylaxis, Supportive Treatment and Increased Monitoring

---

Unless expressly indicated elsewhere in this section, increased monitoring, prophylaxis, and ancillary treatment after any toxicity is left to the clinical judgment of the investigator and must be compliant with Section 6.2 Concomitant Medications.

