**NOTE: See Section 6.1 for required and recommended prophylaxis and management.**

#### 7.1.1 Neurosurgery Toxicities

---

Bleeding, infection, headache, seizures, cerebral edema, pain, changes in neurologic function, thromboembolism.

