#### 7.1.7 Criteria for First Administration of Irinotecan

For Cycle 1 Day 3 irinotecan administration, the participant must have recovered well from any immediate post-operative effects **and** requires no more than 16 mg/day of dexamethasone. Otherwise the participant will be removed from treatment. Criteria found in 7.2.4 also apply.

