**Table 7.2.4 Criteria for Disrupting Treatment, Dose Modification or Discontinuation**

Adverse Event	Agent most likely attributed to toxicity	Treatment modification
Immune Response to NSCs (i.e. development of a new neurologic deficit not attributed to the location of brain tumor, fever without localizing source of infection, new or progressive rash, cough etc.)		
Grade 2 allergic reaction to the NSCs.  NOTE: a decision to stop study treatment will be based on development of clinical signs/symptoms of an immune response rather than a particular level of anti-NSC T cells or antibodies.	NSCs	
Hold study treatment.
 
Initiate immunological testing: Take 3-5 ml of blood in red top tube, kept upright at room temperature until delivery to CICSL. Store at 4 C after sample clots if unable to deliver sample the same day. Take additional samples (at least one additional sample) every two days.
 
Initiate supportive care: Restart dexamethasone to a dose of 4 mg twice daily; if patient is already taking dexamethasone, then increase dexamethasone to at least 4 mg twice daily.
 
Hold study treatment until sign/symptoms <math>\leq</math> grade 1, and resume treatment at the same dose, while continuing dexamethasone at a dose determined by the discretion of the treating investigator in consultation with the PI.

Grade 3 or 4 allergic reaction to NSCs  NOTE: a decision to stop study treatment will be based on development of clinical signs/symptoms of an immune response rather than a particular level of anti-NSC T cells or antibodies.		Hold study treatment.  Initiate immunological testing: Take 3-5 ml of blood in red top tube, kept upright at room temperature until delivery to CICSL. Store at 4 C after sample clots if unable to deliver sample the same day. Take additional samples (at least one additional sample) every two days.  Initiate supportive care: Restart dexamethasone to a dose of 4 mg twice daily; if patient is already taking dexamethasone, then increase dexamethasone to at least 4 mg twice daily. Continue dexamethasone until event resolves to $\leq$ Grade 1, and thereafter at a dose determined by treating investigator as clinically indicated.  If an immune response to the NSCs is considered at least possible, discontinue study treatment
Hematological Toxicities		
Thrombocytopenia Grade 1 ( $75 \times 10^9/L < LLN$ )	Irinotecan	Maintain treatment

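### Dexamethasone 4 mg twice daily is a maximum in Section 6.1.6 but a minimum in Table 7.2.4 for patients already taking it, and no text says which prevails

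*Combined protocol and SAP*

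**What the plan says.** Section 6.1.6, whose heading marks it as required, covers a grade 2 or higher immune response to the NSCs. Participants "will take dexamethasone to a maximum dose of 4 mg twice daily until symptoms resolve" to grade 1 or below.

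Table 7.2.4 covers the same event under its immune-response heading, in a grade 2 row and a grade 3 or 4 row. Both rows tell staff to restart dexamethasone at 4 mg twice daily. Both then add: "if patient is already taking dexamethasone, then increase dexamethasone to at least 4 mg twice daily".

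Two other places show what doses a patient may already be taking. The criteria for the first irinotecan dose (numbered 7.1.7 in the text, cross-referenced elsewhere as 7.2.3) admit a patient who "requires no more than 16 mg/day of dexamethasone". Section 5.5, on removal from treatment, stops a patient who at that point "requires more than 16 mg/day of dexamethasone to control cerebral edema".

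**The concern.** These are two operative safety instructions for one event, and they set opposite limits at the same dose. Staff treating a reaction in a patient already on steroids cannot tell from the protocol whether 8 mg/day is the most or the least they should give.

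The population makes this a practical question. Patients have just had a craniotomy or biopsy for recurrent high-grade glioma, perioperative corticosteroids follow standard of care, and Section 5.5 names cerebral edema as the reason for dexamethasone. The signs that the protocol lists for an immune response include a new neurologic deficit. A ceiling applied literally could reduce or cap steroids when the patient may need them most. A dose above 8 mg/day would follow the table but could be recorded as a departure from Section 6.1.6.

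**Working it through.** The plan has no statistical figure to reproduce here. The check compares the two texts and then looks for a rule that ranks them.

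**Same event?** Section 6.1.6 speaks of an immune response and the table rows of an allergic reaction. The rows stand under the table's heading for immune response to the NSCs, and their grades (2, and 3 or 4) match the 6.1.6 threshold of grade 2 or higher. They address the same event.

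**Common unit.** 4 mg × 2 = 8 mg/day. Let D be the daily dose during the reaction and E the daily dose already being taken.

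- Section 6.1.6, read literally: D ≤ 8.
- Table 7.2.4, patient already on dexamethasone: D ≥ 8.
- Table 7.2.4, patient not on dexamethasone: D = 8.

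**Where they agree and conflict.**

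- Not on dexamethasone (E = 0): the table fixes 8 mg/day, and 6.1.6 permits 8 mg/day or less. The texts are compatible, though not identical.
- On dexamethasone, E ≤ 8, needing no more than 8: D = 8 satisfies both. It is the only dose that does.
- On dexamethasone, needing more than 8: the table permits it and literal 6.1.6 does not.
- On dexamethasone, E > 8: the table's floor is already met, so it requires no change. Literal 6.1.6 requires a cut of E − 8.

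**Illustration.** At E = 16 mg/day, the highest dose accepted at the Cycle 1 Day 3 check, the literal cut is 16 − 8 = 8 mg/day, and 8/16 = 50%. The 16 mg/day figure is a condition for that one irinotecan dose. It does not limit dexamethasone later in treatment, when repeat NSC doses are given, and it is not typical dosing. The 50% is therefore an example, not a bound.

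**Is there a rule of precedence?**

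- The note at the head of Section 7.1 tells readers: "See Section 6.1 for required and recommended prophylaxis and management". It is a cross-reference and does not say that Section 6.1 overrides the table's dose.
- The opening of Section 6.1 reads: "Unless expressly indicated elsewhere in this section, increased monitoring, prophylaxis, and ancillary treatment after any toxicity is left to the clinical judgment". That leaves matters to judgment only where the section is silent, and 6.1.6 gives an express instruction.
- Section 6.2 broadly allows concomitant treatment needed for the patient's care, and it exempts corticosteroids from the ban on immunosuppressants. It does not address the 6.1.6 dose.
- The general dose-modification rules (cross-referenced as 7.2.1) let the principal investigator vary holds and reductions of the study agents, not dexamethasone.

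None of these settles which limit applies.

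**The case against.** The strongest reply is that a strict ceiling was probably never intended. Section 6.2 places no bar on corticosteroid doses above 8 mg/day, and a sensible clinician would be unlikely to cut edema steroids during a reaction. Only patients already on dexamethasone who have a grade 2 or higher reaction are exposed to the conflict. Section 7.1.2 reports no grade 3 or 4 toxicity attributed to the parent NSC line, although it warns that immune responses may occur. All of this stands, and it limits the practical weight of the point. It does not remove the conflict, because a general permission does not override a specific instruction marked as required.

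A reader might infer two further things that the documents do not support.

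- *That it is unclear when investigator discretion over dexamethasone begins.* Section 6.1.6 first gives the dose until resolution, and only then says that for patients still receiving NSCs "dexamethasone should continue at a dose determined by the treating investigator and per consultation with the principal investigator". Both table rows hold study treatment during the event, so that sentence concerns dosing after it. The grade 2 row ties investigator dosing to resuming treatment. The grade 3 or 4 row places it after resolution: "and thereafter at a dose determined by treating investigator as clinically indicated". The timing is clear enough. It also means that this discretion cannot be used to settle the dose during the reaction.
- *That 6.1.6 caps only dexamethasone added for the reaction, so a patient on 16 mg/day would have a ceiling of 16 + 8 = 24 mg/day.* The section does not describe its maximum as an amount added to an existing dose, and the sum takes the Day 3 condition as a baseline dose. The figure should not be attributed to the protocol.

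**Conclusion.** The inconsistency is real. For patients already taking dexamethasone, 8 mg/day is a maximum in Section 6.1.6 and a minimum in both immune-response rows of Table 7.2.4, with no text to rank them. It takes effect for those above 8 mg/day and for those who need more than 8 mg/day.

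The conclusion rests on reading 6.1.6 literally and on treating the table rows as covering the same event, which their heading supports. The number of patients affected cannot be derived from the documents and is probably small.

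This is a matter of patient safety and clear drafting. No sample size, error rate or planned analysis changes, and no claim is made about DLT counts. It should be corrected because the instruction may be needed at short notice and the correction is simple.

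**What to change.** In Section 6.1.6, replace the maximum with the Table 7.2.4 instruction: start or restart dexamethasone at 4 mg twice daily and, for a patient already taking it, give at least 4 mg twice daily. The clinical team should first confirm that the table is the intended rule.

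If the team does want an upper limit, state it in the same words in Section 6.1.6 and in both rows of Table 7.2.4, and say whether it includes dexamethasone already being given for edema.

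The cost is one sentence of protocol wording in 6.1.6, plus matching text in the table only if a limit is intended. Procedures, data collection and analyses are unaffected.

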#### **6.1.7 Prophylaxis and management of cholinergic irinotecan-related syndrome**

Patients may experience an acute syndrome of lacrimation, diaphoresis, abdominal cramping, and diarrhea (early diarrhea) during or shortly after irinotecan administration; this syndrome is thought to be cholinergically mediated. Prophylactic or therapeutic administration of atropine should be considered in patients experiencing cholinergic symptoms.

#### **6.1.8 REQUIRED Serum electrolyte abnormalities $\geq$ CTCAEv3 grade 3**

If serum chemistries  $\geq$  CTCAEv4 grade 3 or greater:

Patient's potassium, calcium, phosphorous or magnesium should be immediately supplemented or otherwise corrected following the availability of those laboratory results, in order to minimize the time patients have abnormal values.

More frequent testing should be done if clinically indicated, e.g. patient has had prior low values, patient is experiencing gastro-intestinal toxicities or is taking medications that can result in lowering of their potassium, magnesium, phosphorus or calcium levels.

## **6.2 Concomitant Medications**

Participants must be instructed not to take any additional medications (including over-the-counter products) during the trial without prior consultation with the investigator. All medications taken within 30 days of screening should be recorded. If concomitant therapy must be added or changed, including over-the-counter medications or alternative therapies, the reason and name of the agent/therapy should be recorded.

In general, the use of any concomitant medication/therapies deemed necessary for the care of the participant are allowed, including drugs given prophylactically (e.g. antiemetics) with the following exceptions:

- No other investigational therapy should be given to patients
- No anticancer agents other than the study medications administered as part of this study protocol should be given to patients. If such agents are required for a patient then the patient must first be withdrawn from the study.
- CYP3A4 Inducers and Moderate to Strong Inhibitors: Because concomitant use of CYP3A4 hepatic enzyme inducing anticonvulsants can result in decreased blood levels of irinotecan, the following anticonvulsants are not allowed while the patient is participating in treatment phase of this study: phenytoin (Dilantin), fosphenytoin (Cerebyx), carbamazepine (Tegretol), phenobarbital (Luminal, Solfoton), primidone (Mysoline), and oxcarbazepine (Trileptal).

Additionally, patients must not take other medications that are moderate to strong CYP3A4 inhibitors or strong inducers (Table 6.2) while undergoing study treatment.

**Table 6.2 CYP3A4 Inhibitors and Inducers**

Strong CYP3A4 Inhibitors ( $\geq 5$ -fold increase in AUC)	Moderate CYP3A4 Inhibitors ( $\geq 2$ -but $< 5$ -fold increase in AUC)	Strong CYP3A4 Inducers
Atazanavir Clarithromycin Indinavir Itraconazole Ketoconazole Nefazodone Nelfinavir Ritonavir Saquinavir Telithromycin Suboxone	Amprenavir Aprepitant Diltiazem Erythromycin Fluconazole Fosamprenavir Grapefruit juice Pomegranate juice Verapamil	Aminoglutethimide Bexarotene Bosentan Carbamazepine Efavirenz Fosphenytoin Griseofulvin Modafinil Nafcillin Nevirapine Oxcarbazepine Phenobarbital Phenytoin Primidone Rifabutin Rifampin Rifapentine St. John's wort

If over the course of study treatment the patient receives any of these drugs, efforts should be made to discontinue the use of inhibitors or potent inducers as soon as possible. Such patients may continue study treatment only at the discretion of the principal investigator. Patients who cannot be discontinued from use of a prohibited CYP3A4 inducer or inhibitor must be removed from the treatment phase of the study.

- Use of flucytosine (5-FC) during study treatment is also not allowed. These NSCs also have the ability to convert 5-FC to 5-fluorouracil, but the safety of the combination of 5-FC and irinotecan in brain tumor patients being treated with these NSCs is unknown at this time.
- Use of drugs known to **inhibit** UGT1A1, such as Atazanir, Gemfibrozil, Indinavir, or Ketoconazole, are prohibited while undergoing study treatment as they are likely to increase SN-38 levels and increase overall toxicity to irinotecan.
- Co-medication that may interfere with study results; e.g. immuno-suppressive agents other than corticosteroids, such as systemic cyclosporine and tacrolimus are prohibited during the treatment phase of the study.
- Use of herbal medications may have unknown interactions with the metabolism of the study agents, and therefore are prohibited from use during the treatment phase of the trial.

## 7 EXPECTED TOXICITIES AND DOSING DELAYS/DOSE MODIFICATIONS

---

### Anticipated Toxicities

---

**NOTE: See Section 6.1 for required and recommended prophylaxis and management.**

#### 7.1.1 Neurosurgery Toxicities

---

Bleeding, infection, headache, seizures, cerebral edema, pain, changes in neurologic function, thromboembolism.

#### 7.1.2 NSCToxicities

---

All toxicity studies to date in mice have shown no evidence of organ damage or tumorigenicity due to hCEm16-NSCs.

In the first-in-human study of HB1.F3.CD.NSCs (i.e., the parent cell line that was adenovirally transduced to create the hCEm16-NSCs being studied in this clinical trial), no grade 3 or 4 toxicities attributable to the NSC were observed.

Immune responses to other cellular or gene therapy agents have occurred and may occur to hCEm16-NSCs.

#### 7.1.3 Microdialysis Catheter Toxicities

---

Bleeding along the catheter tract, infection localized to or clearly emanating from the catheter. Minor bleeding (less than 1 mL) has been observed in 3% of patients (Poca et al., 2006), and there have been no documented microdialysis catheter-related infections.

#### 7.1.4 Irinotecan Toxicities

---

##### **Common:**

Neutropenia and/or late diarrhea (occurring more than 8 hours after irinotecan administration) are common dose-modifying toxicities.

Other commonly observed adverse events include nausea and vomiting, anorexia, weight loss, abdominal cramping, constipation, alopecia, asthenia, lymphocytopenia, anemia, fever, and dehydration as a result of diarrhea and/or vomiting.

Patients may experience an acute syndrome of lacrimation, diaphoresis, vasodilation (flushing), abdominal cramping, and diarrhea (early diarrhea) during or shortly after irinotecan administration; this syndrome is thought to be cholinergically mediated.

**Less common:** mucositis, colitis (sometimes with gastrointestinal bleeding), skin irritation at infusion site, headache, dizziness, confusion, somnolence, flatulence, dyspepsia, rash, minor infection

**Rare, but serious:** pulmonary toxicity (manifested as shortness of breath, non-productive cough, and transient infiltrates on chest x-ray), elevated hepatic enzymes, increased serum creatinine, thrombocytopenia, infusion reaction, neutropenic infection, febrile neutropenia

## Dose Modifications/Delays/Start of Cycle Criteria

---

### 7.1.5 General Information

---

1. The study will use the NCI Common Terminology Criteria for Adverse Events (CTCAE) version 4.0 to grade toxicities. A copy of the version 4.0 can be downloaded from:  
<http://evs.nci.nih.gov/ftp1/CTCAE/About.html>
2. Whenever treatment is held pending resolution of toxicity to grade 1 or return to baseline, this criterion may also be met if the toxicity resolves to within 1 grade of the baseline value for a pre-existing laboratory abnormality. Baseline values are from screening assessments.
3. Study agents are always held together, regardless of the attribution of the toxicity.
4. NSC or irinotecan dose re-escalation is never permitted in this study.
5. If, for the best interest of the patient, the investigator wants to hold the study agent(s) or dose reduce (including increasing the dose reduction) after an adverse event in a manner not outlined in Table 7.2.4, this is permissible following discussion with and written approval the Principal investigator.\*
6. For situations where a participant experiences a toxicity which the treating investigator feels is unlikely related to treatment with either study agent, but which requires hold or reduction of either agent according to Table 7.2.4, maintaining treatment or maintaining treatment dose is allowable per discussion with and written approval by the Principal Investigator.\*
7. For holds due to toxicities related to study agent(s), if the participant does not meet criteria to resume treatment within 28 days of their last NSC administration (or irinotecan for Dose Level 1/1 participants after they have completed cycle 1), the participant must permanently discontinue study treatment (both agents). However, if the participant is clearly benefiting from the study, the investigator may contact the Principal Investigator to determine if the participant can remain on study and at what dose level. Agreement of the Principal Investigator is to be documented in writing.\*
8. For holds for reasons other than treatment related toxicities, such as inclement weather or adverse events unrelated to study agents, if the participant does not meet criteria to resume treatment within 28 days of their last NSC administration, the study agent(s) may be restarted with written approval from the Principal Investigator, as long as there has been no significant evidence of disease progression during the treatment interruption.\*
9. Section 7.3 details resuming agent administration following a treatment hold.

\*The principal investigator will document assessment of the impact of these determinations on the study design, objectives and endpoints or risk to participants. If any modifications to the treatment plan might affect the study design, objectives, and endpoints, or impact the risk of participants, a single subject exception will be sought by the IRB. If the treating investigator is the principal investigator, the determination and the rationale for the determination will clearly be documented in the medical record.

### 7.1.6 Start of Cycle Criteria

---

In order to proceed with the next cycle of study treatment:

- a) adverse events (except for alopecia) that occurred in the preceding cycle must have improved to a CTCAE v 4.0 grade  $\leq 1$  (or within 1 grade of starting values for pre-existing laboratory abnormalities),
- b) ANC must be  $\geq 1500$  cells/mm^3,

- c) platelet count  $\geq 100,000 \text{ cells/mm}^3$ , and
- d) treatment-related diarrhea has resolved.

For participants who received two administrations of NSCs with irinotecan (or irinotecan only for participants in dose level 1/1  $\geq$  cycle 2) in the previous treatment cycle, a delay of up to 14 days in starting the next cycle is allowed in order for the patient to have time to recover from toxicities of the prior cycle.

